### Population for Overall Aim:

For the primary analysis comparing QD to BID patients, we will consider those patients who initiated tofa 5 mg BID on or after February 2016 and those that initiated tofa 11 mg QD after it became available in February 2016. Although the sample size will be smaller than if we consider all tofa 5 mg BID patients, the addition of those patients may introduce noise since there is the possibility that they could differ from the more recent initiators. Therefore, we will consider the cleaner cohort of all patients initiating tofa on or after February 2016.

In order to adequately measure the outcome, the initiators will also be required to have a follow-up visit at 6 months (+/- 3 months) after tofacitinib initiation.

The data cut to be used will be the most recent available.

With regards to dosing, patients can be categorized as follows:

QD dosing: once-daily tofacitinib 11mg

BID dosing: 5mg twice-daily

Other: other dosages including 10 mg and will also include not specified

Those in the "other" category will not be considered in these analyses.

The first initial look at the data has indicated that the tofa 5 mg BID group differs on some characteristics from the tofa 11 mg QD group. To account for these differences, in a second look at the data, we propose to consider models adjusted for no more than 10 covariates. This will provide a robust analysis, while preserving sample size. The full propensity score analysis will be done in the final look at the data when the sample size is large enough (as per preliminary power calculations on page 23).

In this second look with adjusted models, we propose to consider covariates with standardized differences > 0.2 as well as age, gender, CDAI and duration of RA (e.g. gender, age, duration of RA, current statin use, prior cDMARD use, prior non-TNF use, current concomitant therapy, CDAI and EQ-5D) in adjusted models. When considering change in outcome, we will also include the baseline level of that covariate in the model (e.g. for change in CDAI, consider baseline CDAI). For the continuous outcomes, mean differences within subject adjusted for covariates will be assessed using linear regression models (least squares means and 95% CIs). For binary outcomes, we will consider multivariable logistic regression models (ORs and 95% CIs). For the primary outcome, the adjusted OR (95% CI) will give the odds of having MCID improvement in the 11 mg QD initiator group as compared to the odds in the 5 mg BID initiator group after adjusting for covariates; the 5 mg BID initiator group will be the reference group. The interpretation will be similar for the other binary secondary outcomes. Please refer to **Table 2\_adj** for the primary outcome and **Table 3\_adj** for the secondary outcomes.

#### **Secondary Descriptive Aim:**

Consider patients that switched from tofa 5 mg BID to tofa 11 mg QD (“switchers”). Patients will be considered to have switched from 5 mg BID to 11 mg QD if they initiated 5 mg BID and subsequently changed their dose to 11 mg QD. These patients would necessarily have to be considered after February 2016.

#### **Secondary Descriptive Analysis:**

Consider the patients that switched from tofa 5 mg BID to tofa 11 mg QD as a descriptive cohort and assess efficacy in these patients. Due to sample size limitations (about 50 switchers available through 4/1/2017 data), we would not perform a formal comparison to a matched cohort, but would generally compare the efficacy rates obtained in the group of switchers to what would be expected of tofa initiators overall based on historical data CCI.

**Table 4** will present patient and disease characteristics of the “switchers”. **Table 5** will present outcomes at 6 months after the time of switch from 5 mg BID to 11 mg QD. In addition to the outcomes presented in **Table 3**, an outcome measuring whether patients’ CDAI values worsen by at least one category from time of switch to 6 months post-switch will be added to **Table 5**.

Statistical analyses will be performed using SAS Version 9.4 (SAS Institute, Cary, NC) and STATA Version 15 (StataCorp, LP, College Station, TX).

**Overall Definitions:**

Tofacitinib Initiation: A tofacitinib initiation is defined as the first ever use of tofacitinib (reported by the rheumatologist). At enrollment in Corrona a detailed medication history is captured for all RA-related medications.

Line of therapy: For the purposes of these analyses, line of therapy will be aligned with the definition provided for previous Pfizer reporting.

1st line: Naïve to conventional synthetic DMARD-IR (csDMARDs) and all Biologic DMARDs

2nd line: Conventional synthetic DMARD-IR, but biologic naïve

3rd line: Biologic DMARD-IR

4th + line: ≥2 Biologic DMARD-IR

Race and Ethnicity: patient self-reported race and ethnicity from the Corrona patient enrollment form.

History of Malignancy: all except non melanoma skin cancer.

History of CVD: Includes history of hypertension (HTN), coronary artery disease, cardiac revascularization procedure (CABG, stent, angioplasty), ventricular arrhythmia, cardiac arrest, myocardial infarction (MI), acute coronary syndrome, congestive heart failure (CHF), unstable angina, stroke, TIA, other CV events, deep vein thrombosis, peripheral artery disease, pulmonary embolism, peripheral arterial thrombosis, urgent peripheral revascularization and peripheral ischemia/gangrene, hyperlipidemia or carotid artery disease (CAD).

**Shell Tables**

**Figure 1. Flowchart of study population.**

N=XX aged 18+ patients with RA  
 N=XX Tofacitinib initiations  
 N=XX 11 mg QD initiations  
 N=XX 5 mg BID initiations  
 N=XX switchers from 5 mg BID to 11 mg QD

**Table 1. Patient Demographic and Clinical Characteristics for Tofacitinib Initiators by Dose (11 mg QD and 5 mg BID)**

At time of Tofacitinib initiation	11 mg QD N=	5 mg BID N=	Standardized difference
Patient Characteristics			
Female: n (%)			
Age: Mean ± SD			
Duration of RA: Mean ± SD			
Race: n (%)			
White			
Black			
Asian			
Other			
Race: n(%)			
White			
Non-white			
Weight: Mean ± SD			
BMI			
Normal/underweight: n (%)			
Overweight: n (%)			
Obese: n (%)			
Comorbid conditions: n (%)			
Hx of Hypertension			
Hx of Diabetes			
Hx of Malignancy*			
Hx of CV disease**			
Current use of statins			
RA Treatment History			
Prior number of cDMARDs: Median (IQR)			
Prior cDMARD use			
0			
1			
2			
3+			

**Table 1 continued**

At time of Tofacitinib initiation	11 mg QD N=	5 mg BID N=	Standardized difference
Prior TNF Use			
0			
1			
2+			
Prior non-TNF Use			
0			
1			
2+			
Prior Biologic Use			
0			
1			
2			
3+			
Current concomitant therapy			
Monotherapy			
Combo w/MTX alone			
Combo w/other cDMARD (not MTX)			
Combo w/MTX + other cDMARD			
Current medication at the time of initiation			
Prednisone use: n (%)			
Prednisone dose among users			
≤10 mg			
>10 mg			
Disease Activity: Mean ± SD			
Tender Joint Count (28)			
Swollen Joint Count (28)			
Physician Global Assessment (0-100)			
Patient Global Assessment (0-100)			
CDAI			
Disease activity category			
Remission (CDAI ≤ 2.8)			
Low (2.8 < CDAI ≤ 10)			
Moderate (10 < CDAI ≤ 22)			
Severe (CDAI > 22)			
Patient Pain (0-100)			
Patient reported fatigue (0-100)*			
EQ-5D (0-1)			
mDAS: Mean ± SD			
DAS ESR: Mean ± SD			
DAS CRP: Mean ± SD			

**Table 1 continued**

At time of Tofacitinib initiation	11 mg QD N=	5 mg BID N=	Standardized difference
Line of therapy			
1 st			
2 nd			
3 rd			
4 th			

SD = Standard Deviation

IQR = Interquartile Range: 25th percentile, 75th percentile

Standardized differences rather than p-values can be more informative regarding the actual size of the difference between the two groups; hence, it is suggested that they be used rather than p-values to inform which variables are to be included in the propensity score model.

\*The scale ranges from 0-100 with 0 being fatigue is no problem to 100 fatigue is a major problem.

**Table 1a. Patient Demographic and Clinical Characteristics for Tofacitinib Initiators by Dose (5 mg BID and 11 mg QD) after Propensity Score Matching.**

Repeat Table 1 in the Propensity Score Matched cohort. *Table only generated for the final analysis.*

**Table 2: Primary outcome of 11 mg QD vs. 5 mg BID Initiators**

*Table generated “after propensity score matching” only for the final analysis.*

	11 mg QD Initiators N=	5 mg BID Initiators N=	p-value*
Primary Outcome	Response Rate	Response Rate	
MCID Improvement in difference in CDAI from initiation to 6 month visit			

\*The p-value will be reported from the t test of the mean difference between the 11 mg QD and 5 mg BID initiators according to the primary outcome.

**Table 2a: Other outcomes of 11 mg QD vs. 5 mg BID Initiators**

*Table generated “after propensity score matching” only for the final analysis.*

	11 mg QD Initiators N=	5 mg BID Initiators N=	p-value*
Other outcomes	Response Rate	Response Rate	
Switching status**			
% Remained on drug at 6 month visit			
% Discontinued initiated drug and did not start another biologic at/before 6 month visit			
% Switched initiated drug to another biologic at/before 6 month visit			

\*P-value will be from a 2 degree of freedom chi-squared test investigating the relationship between the two treatment arms and the 3 switching status categories.

\*\*The “discontinued initiated drug” category will be defined as discontinuation of tofacitinib without a new biologic started. The “switched initiated drug” category was defined as discontinuation of tofacitinib with a new biologic started.

**Table 2b: Additional information on MCID improvement**

*Table generated "after propensity score matching" only for the final analysis.*

	11 mg QD Initiators N=	5 mg BID Initiators N=
Measure	Response Rate	Response Rate
Percent achieving MCID $\geq 2$ if CDAI at initiation is low (CDAI $\leq 10$ )		
Percent achieving MCID $\geq 6$ if CDAI at initiation is moderate ( $10 < \text{CDAI} \leq 22$ )		
Percent achieving MCID $\geq 11$ if CDAI at initiation is high ( $> 22$ )		

**Table 3: Secondary outcomes of 11 mg QD vs. 5 mg BID**

Table generated "after propensity score matching" only for the final analysis.

	11 mg QD Initiators N=	5 mg BID Initiators N=	p-value*
Continuous outcomes	Mean ± SE	Mean ± SE	
Change from baseline CDAI to 6 month CDAI			
Change from baseline mHAQ to 6 month mHAQ			
Change from baseline HAQ to 6 month HAQ			
Change from baseline mDAS to 6 month mDAS			
Change from baseline DAS ESR to 6 month DAS ESR			
Change from baseline DAS CRP to 6 month DAS CRP			
Change from baseline pain VAS (0-100) to 6 month pain VAS			
Change from baseline fatigue (0 to 100) to 6 month fatigue			
Change from baseline EQ-5D (0-1) to 6 month EQ-5D			
Binary outcomes measured at 6 months	Response Rate	Response Rate	
Achievement of LDA †			
Achievement of LDA ‡			
Achievement of Remission §			
Achievement of Remission 			
Improvement in mHAQ $\geq$ 0.25 ¶			
Improvement in HAQ $\geq$ 0.22 ¶			
mACR20 **			

	11 mg QD Initiators N=	5 mg BID Initiators N=	p-value*
mACR50 ***¶			
mACR70 **			

\*The p-value will be reported from the t test of the mean difference between the 11 mg QD and 5 mg BID initiators according to each continuous secondary outcome. Binary outcome p-values will be calculated from chi-squared tests comparing the two groups.

† Low Disease Activity defined as 6-month CDAI≤10 among those with baseline CDAI>10

‡Low Disease Activity defined as 6-month CDAI≤10 for all patients

§Remission defined as 6-month CDAI≤2.8 among those with baseline CDAI>2.8

¶Remission defined as 6-month CDAI≤2.8 for all patients

¶Improvement in mHAQ will be calculated only for patients with baseline mHAQ≥0.25, and improvement in HAQ will be calculated only for patients with baseline HAQ≥0.22

\*\* modified ACR: based on 2 out of 4 measures (not using ESR or CRP)

CCI

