Based on factors in **Table 1** that differ between the two groups (e.g. standardized difference > 0.1) and clinical input on a priori factors to include, a propensity score will be estimated for propensity of being in the 11 mg QD group. A small number of factors will be considered in the propensity score model; these may include age, gender, disease activity, line of therapy, etc. The primary purpose of the propensity score approach is to determine the patients with “common support” – those patients falling in an overlapping distribution of the propensity score. Patients falling outside the common support would have no comparable patients in the other group and would not be able to be used for comparative analyses.

Here we describe the propensity score matching approach.

***Propensity Score Matching Approach:*** To balance differences in baseline patient and disease characteristics among the 5 mg BID and 11 mg QD groups, we will use matched propensity scores.

***Logistic regression model approach to obtain propensity scores:*** We will use the logistic regression approach (outcome is 11 mg QD therapy) including variables such as the following covariates: age (continuous), gender (male is reference group), baseline CDAI (continuous), line of therapy (categorical), duration of disease (categorical), as appropriate. As mentioned above, we plan to examine all the Table 1 variables, but expect that only a select group will be considered in the propensity score model. The resulting logit model will be of the form:

$$\ln\left(\frac{p}{1-p}\right) = m_{11mgQD}$$

$$= \beta_0 + \beta_1 * age + \beta_2 * gender + \beta_3 * CDAI + \beta_4 * line\ of\ therapy + \dots$$

where  $p$  is the probability of 11mg QD Tofacitinib therapy.

A patient's resulting propensity score from the model is the patients predicted 11 mg QD Tofacitinib ( $p_{11mgQD}$ ), given by

$$p_{11mgQD} = \frac{e^{m_{11mgQD}}}{1 + e^{m_{11mgQD}}}$$

After the propensity score model is fit, **Table 1** will again be constructed with this propensity score matched sample and presented in **Table 1a** to ensure that there are no longer any statistically significant differences between the two groups (11 mg QD and 5 mg BID therapy). For the propensity score matching, it is proposed that a caliper of 0.01 will be used, but the caliper may be increased if the resulting sample size available from the propensity score matching is prohibitive.

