### DAS28 and mDAS28:

DAS28 is an indicator of disease activity that is calculated using a weighted combination of four measures: tender joint counts (0-28), swollen joint counts (0-28), erythrocyte sedimentation rate (ESR) and patient reported global health assessment (0-100). The DAS28 range was 0 to 9.4. Laboratory values were not required in the Corona registry, so this information is missing for many of our patients. Therefore, we suggest that a modified DAS28 measure be used instead. This measure is also a weighted combination of measures: tender joint counts (0-28), swollen joint counts (0-28), modified health

assessment questionnaire (mHAQ) measure (0-3), patient reported pain (0-100), physician reported global health assessment (0-100) and patient reported global health assessment (0-100). As [name] mentioned, we have published a manuscript validating the mDAS for use in place of the DAS measure (Bentley, Greenberg and Reed, The Journal of Rheumatology, 2010).

The mDAS28 ranges from 0-9.4 and higher scores indicate higher disease activity.

ACR20/50/70 and mACR20/50/70:

ACR20 is defined as a composite endpoint; if a patient has a response, then he/she shows at least a:

- 20% improvement in tender joint count and
- 20% improvement in swollen joint count and
- At least a 20% improvement in 3 out of 5 of the following endpoints:
  - Patient pain assessment (0-100)
  - Patient global assessment (0-100)
  - Physician global assessment (0-100)
  - Patient self-addressed disability (0-3) - mHAQ
  - Acute phase reactant (erythrocyte sedimentation rate - ESR or C reactive protein - CRP)

ACR50 and ACR70 are defined in a similar fashion.

Because the measures include laboratory values that were not collected for all patients as part of routine clinical practice, e.g. ESR and CRP, a modified ACR20/50/70 is suggested. The mACR20 is also defined as a composite endpoint; if a patient has a response, then he/she shows at least a:

- 20% improvement in tender joint count and
- 20% improvement in swollen joint count and
- At least a 20% improvement in 2 out of 4 of the following endpoints:
  - Patient pain assessment (0-100)
  - Patient global assessment (0-100)
  - Physician global assessment (0-100)
  - Patient self-addressed disability (0-3) - mHAQ

mACR50 and mACR70 are defined in a similar fashion.

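### HAQ and mHAQ at initiation are the only baselines of Table 3 change outcomes missing from Tables 1 and 1a, so an imbalance in them cannot trigger the SAP's rules and their balance after matching is not shown

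*SAP*

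**What the plan says.** **Outcomes.** SAP Table 3 has nine continuous and nine binary rows. The continuous rows include "Change from baseline mHAQ to 6 month mHAQ" and "Change from baseline HAQ to 6 month HAQ". Two binary rows are responder outcomes with a baseline entry condition; the footnote states "Improvement in mHAQ will be calculated only for patients with baseline mHAQ≥0.25", and sets the matching limit of 0.22 for HAQ. The table footnote assigns t tests to continuous rows and chi-squared tests to binary rows, with no baseline term.

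**Composite outcomes.** In the SAP Appendix, the mDAS28 components include "assessment questionnaire (mHAQ) measure (0-3), patient reported pain (0-100"), and the four mACR supporting measures include "Patient self-addressed disability (0-3) - mHAQ".

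**Baseline tables.** Table 1 lists joint counts, both global assessments, CDAI and its categories, pain, the row beginning "Patient reported fatigue (0-100", EQ-5D, mDAS, DAS ESR and DAS CRP. It has no HAQ or mHAQ row. The whole instruction for Table 1a, apart from its timing, is "Repeat Table 1 in the Propensity Score Matched cohort".

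**Covariate selection.** For the propensity score, Analysis for Overall Aim uses Table 1 factors that differ (standardized difference above 0.1 is the example) together with a priori clinical input, and says "we plan to examine all the Table 1 variables". The second-look models (Population for Overall Aim) use a threshold of 0.2 plus age, gender, CDAI and RA duration, with at most 10 covariates, and add the outcome's own baseline when change is analysed. Addendum Objective 1 defines imbalance by the Table 1 standardized differences; Objective 3 uses the 0.2 threshold.

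**The concern.** The SAP gives as its main design objective that the two groups be shown to be alike before outcomes are compared, and Table 1 is the instrument for that. A variable with no row there has no standardized difference, so it cannot meet a threshold, and Table 1a cannot show whether matching balanced it.

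Baseline disability matters to the HAQ and mHAQ rows in two ways. A change score usually depends on where the patient started. For the responder rows, the baseline score also decides who is in the denominator. A QD-BID difference in these rows of the matched table could therefore come from unequal starting scores, or be hidden by them, and the planned output would not let a reader tell.

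**Working it through.** The documents give no figure to reproduce. The check is a comparison of table contents, followed by an illustration of size.

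**1. Change outcomes in Table 3 against baseline rows in Table 1**

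| Change outcome | Initiation value in Table 1? |
|---|---|
| CDAI | yes |
| mDAS | yes |
| DAS ESR | yes |
| DAS CRP | yes |
| Pain | yes |
| Fatigue | yes |
| EQ-5D | yes |
| HAQ | no |
| mHAQ | no |

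Seven of nine are present; HAQ and mHAQ are the only two missing. No redaction mark sits inside the Table 1 rows. Missing laboratory data do not explain the pattern: DAS ESR and DAS CRP are listed although the SAP says laboratory values are absent for many patients, while HAQ and mHAQ are questionnaire scores.

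**2. Rows affected**

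- Total rows: 9 + 9 = 18.
- Directly dependent on an unlisted baseline: change in HAQ, change in mHAQ, HAQ responder, mHAQ responder = 4.
- Dependent through a component only: change in mDAS, mACR20, mACR50, mACR70 = 4. Table 1 carries mDAS itself, and every mACR component except mHAQ.

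The restricted LDA and remission rows make a useful contrast. Their denominators (baseline CDAI above 10 or above 2.8) can be read from the CDAI categories in Table 1. No baseline row gives the size or balance of the subsets with HAQ ≥0.22 or mHAQ ≥0.25.

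**3. Routes by which baseline HAQ or mHAQ could be handled**

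- Propensity score, imbalance route: closed, since the factors come from Table 1.
- Propensity score, clinical-input route: open, but it commits to nothing and shows no balance.
- Adjusted models, 0.2 rule: the second-look text does not name Table 1, but that is the only planned source of pre-match standardized differences between the dose groups. Addendum Objective 1 names it.
- Own-baseline clause: covers the two change rows of Table 3_adj. It does not clearly cover the responder rows and does not reach matched Table 3.

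**4. Size, under assumptions not in the documents**

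Shift in unadjusted mean change = standardized difference × baseline SD × slope of change on baseline. Assume SD 0.5 and slope 0.2 to 0.4.

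- Standardized difference 0.2: 0.2 × 0.5 × 0.2 = 0.02, up to 0.2 × 0.5 × 0.4 = 0.04. Against the 0.22 HAQ threshold: 9% to 18%.
- Standardized difference 0.3: 0.3 × 0.5 × 0.2 = 0.03, up to 0.3 × 0.5 × 0.4 = 0.06. Against 0.22: 14% to 27%.

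The 0.22 threshold applies to individual patients, so these percentages only give a sense of scale for a shift in group means.

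**5. Could matching leave an imbalance by chance?**

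Assume 1:1 matching that keeps all 153 eligible BID initiators (Addendum Objective 2). The standard error of a standardized difference is about √(2/153) = 0.114. For a variable unrelated to the score, the chance of exceeding 0.1 in either direction is P(|Z| > 0.1/0.114) ≈ 38%. Fewer pairs would raise this; correlation of HAQ with matched covariates such as CDAI would lower it.

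**6. The covariate cap**

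The second-look example list has nine covariates: gender, age, RA duration, statin use, prior cDMARD use, prior non-TNF use, concomitant therapy, CDAI and EQ-5D. Adding one disability score gives 9 + 1 = 10; adding both gives 9 + 2 = 11, above the cap.

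**The case against.** The strongest reply is that this is a small reporting gap with several existing safeguards.

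- **Own-baseline adjustment.** Both change rows are adjusted for baseline in Table 3_adj whatever the imbalance. This stands, and it limits the point to matched Table 3, the responder rows and the balance check.
- **Proxies.** mDAS contains mHAQ, and EQ-5D covers mobility, self-care and usual activities. Both are in Table 1, and EQ-5D is in the example adjustment list. A disability imbalance could show through them. This stands in part: they are indirect and do not give the balance of the score being analysed.
- **Other ways in.** Clinical input may bring HAQ into the propensity score, and the SAP allows the model to be revisited with further covariates if the distributions overlap poorly. So it would be wrong to infer that HAQ cannot enter. What it cannot do is enter because it was seen to be imbalanced.

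Three stronger readings are tempting and are not supported:

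- **Eight of 18 rows are compromised.** Eight rows use HAQ or mHAQ somewhere, but the mDAS row has its own baseline in Table 1. An mACR response needs both joint counts and any two of four measures, so it can be reached with no change in mHAQ.
- **The primary outcome is undermined.** MCID is defined on CDAI alone, and baseline CDAI is a named covariate for the propensity score and the adjusted models.
- **The same omission in Table 4 affects the comparison.** Table 4 describes switchers only, has no standardized differences and feeds no imbalance rule. Its gap is descriptive.

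**Conclusion.** The omission is certain from the SAP text: HAQ and mHAQ are the only change-outcome baselines absent from Table 1, and hence from Table 1a. As a result, an imbalance in them cannot trigger the standardized-difference rules, and balance on them after matching is not reported. Four of 18 secondary rows are directly exposed, and two of those four are already baseline-adjusted in Table 3_adj.

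Whether any bias results cannot be known from the plan. The illustrative shift of about 0.02 to 0.06 rests on an assumed SD of 0.5, slopes of 0.2 to 0.4 and standardized differences of 0.2 to 0.3, and it ignores correlation with matched covariates. This is a modest gap in the secondary analyses, worth closing because closing it is nearly free.

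**What to change.** 1. Add HAQ and mHAQ at initiation to Tables 1 and 1a: mean ± SD, number available, and n (%) with HAQ ≥0.22 and with mHAQ ≥0.25, each with standardized differences.
2. Make both scores eligible under the existing imbalance rules, but use at most one (for example mHAQ, which also enters mDAS and mACR) as a general covariate, so that the example list of nine becomes ten. State whether an outcome's own baseline counts towards the cap. If it does, an outcome whose baseline is not already on the list would make eleven, and one covariate must give way.
3. In the matched analysis, estimate the HAQ and mHAQ change rows by linear regression and the two responder rows by logistic regression, each including the baseline score. The t and chi-squared results can stay alongside.
4. Optionally add the scores to Table 4, for description only.

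The cost is a few table rows and four models. The scores must already be extracted to compute the change outcomes, and the change and responder rows lose no further patients, since they need the baseline score anyway. The one real cost is that patients without the chosen score drop out of other adjusted models if it is selected as a general covariate; the number available in Table 1 would show how many.

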\*\*Improvement in mHAQ will be calculated only for patients with baseline mHAQ $\geq$ 0.25 and improvement in HAQ will be calculated only for patients with baseline HAQ $\geq$ 0.22

††modified ACR: based on 2 out of 4 measures (not using ESR or CRP)

Table 2\_adj will present the primary outcome and Table 3\_adj will present the secondary outcomes for the second look incorporating the adjusted analysis.

**Table 3\_switchers. Number of initiators of 11 mg QD (from the cohort of 11 mg QD initiations considered in Tables 1-3) that switch\* to 5 mg BID by their 6 month follow-up visit.**

\*Switch defined as discontinued 11 mg QD and initiated or restarted 5 mg BID.

**Table 4. Patient Demographic and Clinical Characteristics for the cohort of patients that switched from Tofacitinib 5 mg BID to Tofacitinib 11 mg QD**

At time of Tofacitinib 5 mg initiation	Patients that switched from Tofacitinib 5 mg BID to Tofacitinib 11 mg QD N=
Patient Characteristics	
Female: n (%)	
Age: Mean ± SD	
Duration of RA: Mean ± SD	
Race: n (%)	
White	
Black	
Asian	
Other	
Missing	
Race: N (%)	
White	
Non-white	
Weight: Mean ± SD	
BMI	
Normal/underweight: n (%)	
Overweight: n (%)	
Obese: n (%)	
Missing	
Comorbid conditions: n (%)	
Hx of Hypertension	
Hx of Diabetes	
Hx of Malignancy*	
Hx of CV disease**	
Current use of statins	
RA Treatment History	
Prior number of cDMARDs: Median (IQR)	
Prior cDMARD Use: N (%)	
0	
1	
2	
3 +	
Prior TNF Use	
0	
1	
2+	

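### The final matched Table 3 analyses nine change scores by an unadjusted t test; adjusting each for its own baseline would gain precision at almost no cost

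*SAP*

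**What the plan says.** **Final look.** SAP Table 3 is produced only for the final analysis, in the propensity-matched sample. Its nine continuous rows are changes from baseline in CDAI, mHAQ, HAQ, mDAS, DAS ESR, DAS CRP, pain, fatigue and EQ-5D (for example "Change from baseline EQ-5D (0-1) to 6 month EQ-5D"). Each row gives a mean ± SE per arm and a p-value. The footnote takes the p-value from the "t test of the mean difference between the 11 mg QD and 5 mg BID initiators according to each continuous secondary outcome". There is no covariate and no column for the difference with its interval.

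**Second look.** The SAP section Population for Overall Aim plans linear regression for continuous outcomes and adds: "When considering change in outcome, we will also include the baseline level of that covariate in the model". Its example is baseline CDAI for change in CDAI, so the rule means each outcome's own baseline. The note below Table 3_adj says that this table "will present the secondary outcomes for the second look incorporating the adjusted analysis".

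**Matching.** The section Analysis for Overall Aim gives example propensity covariates: age, gender and "baseline CDAI (continuous), line of therapy (categorical), duration of disease (categorical), as appropriate". Candidates are Table 1 factors with a standardized difference above 0.1, plus factors chosen on clinical input. On the caliper, "it is proposed that a caliper of 0.01 will be used", and it may be widened. The Table 1 shell, repeated after matching as Table 1a, has rows for seven of the nine outcome baselines. HAQ and mHAQ have none.

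**Addendum.** Table 3_adj is rerun in the full N = 450 population (Objective 1, imbalanced covariates with model selection) and in a propensity-trimmed population (Objective 3: age, gender, RA duration, baseline CDAI and imbalanced covariates). Neither names each outcome's own baseline as a covariate.

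**The concern.** The SAP sets a sound standard for change outcomes at an interim look, and the table reserved for the final look does not state it. Two things follow for the nine secondary comparisons.

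- **Precision.** A change score carries all the noise of the baseline measurement. A model with the baseline in it removes the part that predicts follow-up, so its standard error is no larger and usually smaller.
- **Exposure to residual baseline differences.** If one arm still starts worse on an outcome after matching, it tends to improve more through regression to the mean, and an unadjusted change comparison counts that as a difference between formulations.

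The study's hypothesis is that the two regimens perform similarly. An estimate of the difference with a tight interval is therefore more useful than a p-value, and Table 3 as drawn gives neither the difference nor its interval.

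**Working it through.** **The plan's own figure.** The only power figure concerns the binary primary outcome: 237 analyzable per group for 50% versus 35% meeting MCID, 90% power, alpha 5%. The two-proportion formula, two-sided, gives 227 uncorrected and 240 with continuity correction, so 237 reproduces approximately. It does not bear on the continuous outcomes, for which the SAP states no power or SD.

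**Inputs.** n = 153 per arm is the ceiling for 1:1 matched pairs, from the 153 eligible BID initiators in the addendum; 1:1 matching is assumed. A gap of 0.1 SD is the SAP's own limit for a negligible standardized difference. The baseline to 6-month correlation r (0.3, 0.5, 0.7), equal SDs s at both visits and independent arms are assumptions.

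**Precision.** Per-patient variance:
- change score: 2(1 − r)s²
- baseline-adjusted: (1 − r²)s²
- ratio, adjusted to change: (1 + r)/2

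The SE of the arm difference is √(2 × variance / n).

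| | r = 0.3 | r = 0.5 | r = 0.7 |
|---|---|---|---|
| Variance ratio | 0.65 | 0.75 | 0.85 |
| SE, change t test (SD units, n = 153) | 0.135 | 0.114 | 0.089 |
| SE, baseline-adjusted | 0.109 | 0.099 | 0.082 |
| Fall in SE, 1 − √ratio | 19% | 13% | 8% |
| Equivalent sample, 1/ratio | 1.54 | 1.33 | 1.18 |
| t-test power where the adjusted model has 90% | 74% | 80% | 85% |

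The ratio does not depend on n. The direction does not depend on equal SDs: with baseline SD s0 and follow-up SD s1, the variance saved is (s0 − r·s1)², which is never negative.

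**Shift from a residual gap.** With no formulation effect, a baseline gap d moves the change difference by (1 − r)d in size. At d = 0.1 SD:
- r = 0.3: 0.7 × 0.1 = 0.07 SD, or 0.07/0.135 = 0.52 of the t test's SE
- r = 0.5: 0.05 SD, or 0.44 SE
- r = 0.7: 0.03 SD, or 0.34 SE

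**Effect on false positives.** In 4,000 simulated data sets per setting, with 153 per arm, no true effect and the observed gap held at 0.1 SD, the t test rejected in 4.1%, 4.2% and 4.3% (r = 0.3, 0.5, 0.7). The baseline-adjusted test rejected in 5.4%, 4.9% and 5.2%. The t test does not over-reject here because its SE also allows for baseline variation that a fixed gap removes. If 0.1 SD were instead a systematic gap with sampling variation on top, a normal approximation gives 8.1%, 7.2% and 6.3%.

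**Where balance is controlled.** CDAI, mDAS, DAS ESR, DAS CRP, pain, fatigue and EQ-5D are in Table 1. They are therefore screened at 0.1 and rechecked in Table 1a. HAQ and mHAQ are neither, unless clinical input brings them in. The SAP Appendix says laboratory values are missing for many patients, so DAS ESR and DAS CRP are compared in a subset whose balance Table 1a does not show.

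**The case against.** The best counter-argument is that the adjustment may not be missing. The addendum sets out to repeat the primary analyses, which it lists as running through Table 3_adj. Because that set includes Table 1a, the analyses being repeated appear to be the matched ones. Objective 3 describes adjusting for baseline CDAI as the primary analyses did, and protocol section 9.7 pairs matching with covariate adjustment. On this reading Table 3 is the unadjusted companion of an adjusted table. This stands as a real possibility, and some surrounding text is redacted. A reader might infer that the final analysis abandons baseline adjustment; the documents do not support that. What they support is narrower: no visible text specifies each outcome's own baseline in the matched sample.

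A reader might also infer that of the nine baselines only CDAI is controlled by the propensity score. It is the only one named as an example, but the screening rule reaches seven of the nine. mHAQ is also a component of mDAS, so it is partly covered.

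Finally, comparing well-matched groups without further covariates is a recognised choice. In non-randomised groups, change scores and baseline adjustment rest on different assumptions about how the groups would have evolved, and measurement error in the baseline leaves some bias in the adjusted estimate. This stands too, so adjustment is not free of assumptions. The SAP has, however, already chosen baseline adjustment for these same outcomes at the second look.

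**Conclusion.** The point holds as a cheap improvement of low to moderate priority. The main cost of the t test is precision: its variance is 1.18 to 1.54 times that of the baseline-adjusted analysis for r from 0.7 to 0.3. The secondary cost is a shift of 0.03 to 0.07 SD, only if a gap of 0.1 SD survives matching, and HAQ and mHAQ are the least protected. The sizes rest on assumed correlations and equal SDs; the direction of the precision gain does not.

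It would be tempting to conclude that regression to the mean biases the final comparison or produces false positives. The documents show no post-matching gap on any outcome. At an observed gap of 0.1 SD the t test did not over-reject, and the modest excess under a systematic gap needs an imbalance that nothing in the documents establishes. The binary primary outcome and its sample size are untouched.

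**What to change.** - In the Table 3 footnote, replace the t test for continuous outcomes by a linear regression in the matched sample, with formulation and that outcome's own baseline as terms.
- Add a column for the adjusted mean difference with 95% CI. The unadjusted arm means may stay beside it.
- Add baseline HAQ and mHAQ rows to Tables 1 and 1a, so that both can be screened for the propensity score and checked after matching.
- State which adjusted tables accompany the matched analysis. This settles the ambiguity left by the addendum and protocol section 9.7, and it carries into the repeat on the August 2019 registry version.

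The cost is a footnote change, one regression per row and two table rows. The baselines are already needed to compute the changes. The added assumption is the one the SAP accepts at its second look. There is precedent for revising a shell table's test: addendum Objective 3 adds a chi-square test beside the t test in Table 2. If tables have already been produced, the adjusted results should be reported beside them and dated as an addition.
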